#### **Exclusion Criteria:**

The study is limited to English speakers, as speech perception measures are only available in English so non-native English speakers do not undergo the standard clinical protocol.

For aim 3, parents of English speaking subjects who do not speak English will not be specifically excluded. Due to the high incidence of English speaking children in Spanish speaking homes, for primary guardians who speak Spanish, Spanish materials will be provided. Children who have previous experience with a BAI or bone conduction hearing device will not be included for study.

Subjects will be screened for any allergies related to adhesives as the experimental device requires use of an adhesive adapter. Those reporting allergies to adhesives or highly reactive skin will be excluded from study as a precautionary measure.

#### **Procedures Involved\***

The medical records of patients who received a bone conduction hearing device follow-up between January 1, 2010 through September 23, 2021 will be retrospectively reviewed. We anticipate review of approximately 500 medical records. Demographic data for review include gender, age, primary spoken language, and etiology. Standard clinical hearing outcome data will be reviewed for both groups and will include audiometric thresholds, word recognition ability, and speech perception measures. This information will be used to determine study candidates. Those who meet the inclusion criterion will be contacted for study participation. Once we have received a minimum of 10 but no greater than 30 participants for each study group, retrospective review will be completed and no new charts will be accessed. Participants will then only be studied prospectively. Demographic and audiometric data will be maintained under a unique identifier code linked to the consented study

participant for reference to study outcome data.

### **Study Populations**

- Minimum of 10 established adult unilateral profound sensorineural hearing loss recipients of bone anchored implants
- Minimum of 10 established adult conductive hearing loss recipients of bone anchored implants
- Minimum of 10 new pediatric headband bone conductive device candidates.
- Minimum of 10 guardians of the pediatric population involved
- Minimum of 15 established pediatric unilateral conductive hearing loss patients currently fit with a bone conduction device on a softband.
- Minimum of 10 established bilateral conductive hearing loss patients currently fit with a bone conduction device on a softband.

### **Study Design**

#### **Aims 1&2**

- Experienced adult bone anchored implant recipients with either unilateral profound sensorineural hearing loss or conductive hearing loss will be enrolled for study. Subjects will be given the Adhear hearing system on trial for 2 weeks  $\pm$  90 days. Prior to dispensing of the experimental system, function of the subject's implant system will be verified. Custom pre-post subjective measures will be administered. Subjects will undergo behavioral measures of benefit in the 1) implant aided condition and 2) the Adhear Aided condition
- Conditions will be randomized by subject and will consist of the following:
  - Speech perception in noise ability using the BKBSIN (Etymotic, Elk Grove, IL) adaptive tests for speech front, noise front (0°/0° azimuth), speech poorer ear, noise better ear (90°/270° azimuth), speech better ear, noise poorer ear (90°/270° azimuth)
  - Soundfield aided narrow band signal thresholds – better ear plugged
  - Soundfield aided speech reception thresholds – better ear plugged
- At 2 weeks  $\pm$  90 days, subjects will undergo behavioral measures of benefit in the Adhear aided condition. Tests will be repeated using the subjects own processor on a soft headband to evaluate transcutaneous stimulation.
- Conditions will be randomized by subject and will consist of the following:
  - Speech perception in noise ability using the BKBSIN (Etymotic, Elk Grove, IL) adaptive tests for speech front, noise front (0°/0° azimuth), speech poorer ear, noise better ear (90°/270° azimuth), speech better ear, noise poorer ear (90°/270° azimuth)
  - Soundfield aided narrow band signal thresholds – better ear plugged
  - Soundfield aided speech reception thresholds – better ear plugged

#### **Aim 3**

- Pediatric conductive hearing loss patients who are between the ages of 5 and 15 years of age and present to the UMEI hearing rehabilitation by bone conduction technology along with their primary guardian will be enrolled for study. Subjects will be evaluated in two phases:
  - Phase 1 – random assignment to trial with either a traditional bone conduction

device on a headband or an Adhear hearing system for 3 weeks  $\pm$  90 days. Pediatric and parent subjective questionnaires will be administered prior to and at the end of phase 1.

- Phase 2- trial with system alternate to that which was assigned for phase 1. Pediatric and parent subjective questionnaires will be administered prior to and at the end of phase 2.

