## **Inclusion and Exclusion Criteria\***

All subjects will be prospectively enrolled for study.

Aims 1 and 2 will include adult English speaking patients who are experienced users of BAIs for the

indication of either single sided deafness or conductive hearing loss. Experienced will be defined as greater than 6 months of device use and no intermittent function of the device within 2 weeks of enrollment. Aims 1 and 2 will require retrospective chart review to identify potential study subjects for recruitment. Subjects who spontaneously present to the clinic may also be enrolled should the meet inclusion criteria. Subjects will be limited to those who have normal hearing by bone conduction defined as a pure tone average of 25 dBHL or better at 500, 1000, 2000, & 3000 Hz in at least one ear.

Aim 3 will include English speaking children 5 to 17 years of age and their primary guardian who present to the clinic for treatment by BAI on a headband device for the indications of single sided deafness or conductive hearing loss. Because subjects for aim 3 have not previously been users of a BAIs, subjects for aim 3 will be recruited during spontaneous presentation to the clinic. Subjects will also be recruited for aim 3 from various sites using flyers and email. Subjects will be limited to those who have no prior use of a BAI or bone conduction hearing device, normal hearing by bone conduction defined as a pure tone average of 25 dBHL or better at 500, 1000, 2000, & 3000 Hz in at least one ear. For those children where this cannot be definitively established, children will be included who display clinical signs of normal bone conduction hearing beyond a reasonable doubt and may include such evidence as (but not limited to): auditory brainstem response, speech awareness thresholds, visual reinforcement audiometry, conditioning play audiometry, CT scans, etc.)

Aims 3 a & b are an extension of Aim 3 and will include pediatric bilateral or unilateral conductive hearing loss patients who are between the ages of 2 and 17 years of age and are currently managed by the UMEI with a bone conduction device attached to a softband will be enrolled for study.

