## **Data Management\***

Data collected includes: Gender, age, language, etiology and type of hearing loss, treatment ear, audiometric data including thresholds and speech outcomes, prior hearing treatment, date of activation or device use, aided thresholds, aided speech in noise performance, hours of device use, and subjective outcomes (see questionnaires included).

All the previously described data will be stored on the PI's computer and used for analyses purposes in room 526 of the clinical research building at the University of Miami Medical Center located at [name]. It will be password protected, and unique identifiers will be used for subject protection. Descriptive statistics will be used to report demographic (e.g. age and

gender) data. Quantitative data will be presented as mean, standard deviation (SD) and range (minimum and maximum); qualitative data will be presented as frequencies and percentages. Inferential statistics will be applied to detect differences in speech in noise performance as a function of transcranial attenuation. For this purpose, parametric Student's t-tests or nonparametric Wilcoxon signed rank tests will be performed, depending on the data distribution. Statistical significance will be set to  $p < 0.05$ . The subjective questionnaires will be summarized by visit using descriptive summaries. For numeric measures the change from baseline will be calculated and inferential tests applied. For categorical measures, a shift from baseline will be presented demonstrating the subjects as being better, the same, or worse.

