## **Consent Process**

Due to COVID 19, we also will be consenting remotely. When consenting remotely, we will follow the recommendations provided by both University of Miami and the FDA. Potential subjects will be called and/or emailed for recruitment and if agreed to participate, a zoom meeting and/or RedCap econsenting application will be used for the consenting process; a witness will be present in the zoom call. All steps will be documented in the format attached.

It is possible that while our study is limited to English speaking patients, the parents of some patients included for aim 3 may be non-english speakers. Because only a maximum of 15 subjects will be enrolled for aim 3 it is anticipated that only a small number of subjects (<5) may be enrolled whose guardians will not understand English. Based on population data for Miami-Dade, we expect this to be limited to Spanish speakers. For those participants all required documents will be translated into Spanish. Further a native Spanish speaker and certified medical translator will be present for consent and all test sessions.

When determining whether a child is capable of assenting, the ages, maturity, and psychological state of the child will be taken into account. The PI will consider the child's experience and level of understanding, ensure the child is cooperative and agreeable to participation, and ensure the child's

rights are maintained. As with adult consents, assent will be conducted in a manner and location that ensures participant privacy, Giving adequate information about the study in a language understandable to the participant, Providing adequate opportunity for the participant to consider all options, Responding to the participant's questions, Ensuring the participant has understood the information provided, Obtaining the participant's voluntary agreement to participate, and Continuing to provide information as the participant or research requires.

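### Aim 3 randomises device order in 10 to 15 children but states no balancing of order and no period term, so any phase effect costs power and can shift the realised estimate

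*Combined protocol and SAP*

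**What the plan says.** Under Study Design, Aim 3, the first phase is "random assignment to trial with either a traditional bone conduction" "device on a headband or an Adhear hearing system for 3 weeks" (with a window of 90 days either way). The second phase is "trial with system alternate to that which was assigned for phase 1". Every child therefore tries both devices, and chance decides which comes first.

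- **Size.** Study Populations asks for "Minimum of 10 new pediatric headband bone conductive device candidates". Consent Process sets the upper limit: "Because only a maximum of 15 subjects will be enrolled for aim 3". The separate minimum of 15 in Study Populations belongs to the established unilateral softband users of Aim 3a, whose device order is fixed, and plays no part here.
- **Experience.** Inclusion and Exclusion Criteria, for Aim 3: "Subjects will be limited to those who have no prior use of a BAI or bone conduction hearing device".
- **Tests.** Data Management names Student's t-tests, or "nonparametric Wilcoxon signed rank tests will be performed, depending on the data distribution". That sentence concerns speech-in-noise performance in relation to transcranial attenuation. Questionnaire scores get change from baseline with inferential tests that are not named.
- **Not stated anywhere.** The documents give no randomisation method, block, ratio or counterbalance for Aim 3, and no period, phase or order term in any analysis. Assigned order is not itemised among the data to be collected, although a date of activation or device use is.
- **Aims 1 and 2.** The text reads "Conditions will be randomized by subject and will consist of the following", and the list that follows contains tests and loudspeaker positions.

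**The concern.** In a two-period crossover, each child's Adhear-minus-headband difference contains the device effect plus or minus the phase effect, with the sign set by the order. A phase effect is plausible here. The children start with no device experience, so Phase 2 also carries what they learned in Phase 1. The same outcome measures serve both devices, and with the wide visit window the two assessments can be months apart.

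Randomising the order makes it possible to remove that effect, but only if the analysis uses the order. A one-sample test on the pooled differences does not. With equal order groups, the phase effect is counted as noise and power falls. With unequal groups, part of it is left in the estimate. At 10 to 15 children there is little power to spare, and uneven splits are common under simple randomisation.

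**Working it through.** The plan gives no SD, target effect, phase effect or power, so there is no figure of its own to reproduce.

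**Inputs from the protocol.** n = 10 (Study Populations) to 15 (Consent Process); significance level 0.05 (Data Management).

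**Assumptions.** Two-sided testing; simple 1:1 randomisation, since no method is stated; SD of the within-child difference given order = 1; phase effect π (Phase 2 minus Phase 1) of 0 to 1 SD; true device effect τ of 0.9 or 1 SD.

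**Model.** d = τ + sπ + e, where d is Adhear minus headband, s = +1 if Adhear comes second and −1 if it comes first, and SD(e) = 1.

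**Step 1: how uneven the split can be (exact binomial).**

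- n=10: exactly 5:5, 252/1024 = 0.246; 7:3 or worse, 352/1024 = 0.344; 8:2 or worse, 112/1024 = 0.109.
- n=15: 10:5 or worse, 0.302; 11:4 or worse, 0.119.

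**Step 2: shift in the realised estimate.** The mean of d is τ + π(n1 − n2)/n, with n1 the number who get Adhear second.

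- 7:3 gives 4/10 = 40% of π; 8:2 gives 6/10 = 60%.
- 10:5 gives 5/15 = 33%; 11:4 gives 7/15 = 47%.

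If π = 0.5 SD, the shift is 0.20 SD at 7:3 and 0.30 SD at 8:2. Either order is equally likely to be the larger, so the shift averages to zero over the randomisation.

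**Step 3: added variance.** At 5:5 the expected variance of the pooled differences is 1 + π² × 10/9. This gives 1.28 at π = 0.5 and 2.11 at π = 1, so the SD used by the test rises from 1 to 1.13 and 1.45.

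**Step 4: type I error of the order-ignoring t test (simulation).**

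| Split | π = 0.5 | π = 1 |
|---|---|---|
| n=10, averaged over simple randomisation | 0.051 | 0.052 |
| n=10, 5:5 | 0.031 | 0.006 |
| n=10, 7:3 | 0.060 | 0.063 |
| n=10, 8:2 | 0.106 | 0.200 |
| n=15, averaged over simple randomisation | 0.051 | 0.051 |
| n=15, 10:5 | 0.063 | 0.067 |
| n=15, 11:4 | 0.097 | 0.170 |

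**Step 5: power.** "Ignoring order" is the t test on pooled d, averaged over simple randomisation. "Adjusted" is the mean of the two order-group means on n − 2 degrees of freedom, with a balanced split (5:5 or 8:7).

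| | π = 0 | 0.25 | 0.5 | 1 | Adjusted, any π |
|---|---|---|---|---|---|
| n=10, τ = 0.9 | 72% | 69% | 62% | 42% | about 70% |
| n=10, τ = 1 | 80% | 78% | 71% | 50% | about 79% |
| n=15, τ = 1 | 95% | 94% | 90% | 72% | about 95% |

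The signed rank test behaves the same way: at n=10 and τ = 1 its power is 77%, 76%, 69% and 48%.

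**Step 6: why balance matters as well as adjustment.** The adjusted estimate has variance (1/4)(1/n1 + 1/n2). That is 0.100 at 5:5, 0.104 at 6:4 and 0.156 at 8:2. With no phase effect and τ = 1 at n=10, adjusting under simple randomisation gives 74% power, against 79% with a 5:5 split.

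**The case against.** Several points on the other side are sound.

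- **Size rests on an assumption.** The documents give no phase effect. At 0.25 SD the loss at n=10 is about 3 points (72% to 69% for a 0.9 SD effect), and at zero there is no harm. This stands, and is why a range is shown.
- **No systematic bias.** A reader might infer that the device comparison is biased, or that false positives generally run at 11% to 20%. The documents do not support that. At n=10 those rates belong to an 8:2 split, and 8:2 or worse has probability 0.11. At 7:3 the rate is about 6%, and over the randomisation it is about 5%.
- **Silence is not a decision.** A reader might infer that the sponsor has chosen unbalanced randomisation. The text neither describes nor excludes balancing, so the defect is an unstated rule.
- **No test is assigned to this comparison.** The t and signed rank tests are attached to a different question, and the plan does not say that the t test is paired. The figures above show what happens if the named tests are used for Aim 3. The lack of an assigned test leaves order just as unhandled.
- **Order may be recoverable.** A date of activation or device use is collected. If it is kept for each device, it would show the order. It is wrong to say that the order would be lost, but a derived order is a weaker record than the assigned one.
- **Aims 1 and 2.** The randomised conditions there may be tests and loudspeaker positions and not devices, so the same fault cannot be asserted for those aims.

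These points narrow the concern to Aim 3 and to lost power first. They do not remove it, because the trial will have one realised split and the plan has no way of allowing for it.

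**Conclusion.** The concern holds for Aim 3. The plan randomises the order of two devices in 10 to 15 inexperienced children, states no balancing, and names no analysis that uses the order.

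The main consequence is lost power. At n=10 and a 0.9 SD true effect, it falls from about 72% to 69%, 62% or 42% for a phase effect of 0.25, 0.5 or 1 SD. A balanced, period-adjusted analysis keeps about 70% throughout. The second consequence is a chance shift in the realised estimate, equal to 40% of the phase effect at 7:3 and 60% at 8:2.

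Both depend on a phase effect that is plausible but not given, on simple randomisation, and on the named tests being applied to the pooled within-child differences. The finding is not one of average bias or of a generally raised type I error. The change is worth making before enrolment, because balance cannot be restored afterwards.

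**What to change.** For Aim 3:

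1. Assign device order from a concealed list prepared in advance, in permuted blocks, for example of 4 or of mixed sizes. Blocks of 2 are best avoided: the devices look different, so every second assignment could be predicted. With blocks of 4, the two orders differ by at most 2 children.
2. Record the assigned order as its own data item.
3. State that, for every Aim 3 outcome, Adhear minus headband is estimated as the average of the two order-group means of the within-child difference (equivalently, a mixed model with device and period), with its 95% CI.
4. If normality is doubted, compare the Phase 2 minus Phase 1 differences between the two order groups, by a rank-sum test or by permuting order labels across the groups. These differences centre on π + τ and π − τ, so the contrast is 2τ and the phase effect cancels. Shuffling values within an order group would not work, because it leaves the group means unchanged.

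For Aims 1 and 2, first clarify whether the randomised conditions include the device. If they do, apply the same approach to the device contrasts made within a session.

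The cost is a randomisation list, one data field and a short analysis paragraph. Statistically it is one degree of freedom: about 1 to 2 points of power at n=10 if there is no phase effect and the split is even.

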**Objective and behavioral outcome measures.**

- Data logging of device use
- Soundfield aided narrowband signal thresholds – better ear plugged
- Soundfield aided speech reception thresholds – better ear plugged
- Word recognition ability using PBK words and speech shaped noise at +5dB SNR for soft at 35, 45, and 55 dB for speech front, noise front (0°/0° azimuth)
- Aim 3a  
Pediatric unilateral conductive hearing loss patients who are between the ages of 2 and 17 years of age and are currently managed by the UMEI with a bone conduction device attached to a softband will be enrolled for study. Subjects will be given the ADHEAR bone conduction system on trial for 2 weeks  $\pm$  90 days. Subjects will be evaluated over 2 experimental visits.
  - VISIT 1: Assessment of subject's bone conduction device on the headband and initiation of ADHEAR trial
    - Prior to dispensing of the experimental system, function of the subject's current bone conduction device will be verified.
    - Subjective measures will be administered to determine benefit and satisfaction with the subject's own device on the headband.
    - Subjects will undergo behavioral measures of benefit with own bone conduction device on a headband
    - Subjects will be provided ADHEAR bone conduction hearing system
  - VISIT 2:
    - Subjective measures will be administered to determine benefit and satisfaction with the ADHEAR bone conduction hearing system
    - Subjects will undergo behavioral measures of benefit with ADHEAR bone conduction hearing system
    - ADHEAR system will be returned to the research site upon completion of the trial

**Objective and behavioral outcome measures unilateral conductive hearing loss subjects:**

- Data logging of device use (parent and subject report)
- Soundfield aided narrowband signal thresholds – better ear plugged
- Soundfield aided Ling thresholds – better ear plugged using the DSLio - Ling 6(HL) test (v2.0) which provides calibrated, pre-recorded Ling 6 sounds (m, u, a, i, sh, s) for use in measuring unaided or aided thresholds.
- Soundfield aided speech reception thresholds using Calibrated and pre-recorded Auditec Spondee lists– better ear plugged
- Word recognition ability using the Auditec Inc PBK-50 words. The majority of subjects enrolled are expected to be between the ages of 3 and 7 and the PBK word list offers the most age appropriate assessment of word recognition ability for this age group, while also allowing for accurate assessment of audibility in older children under aided condition. In those children who are not able to repeat words reliably, a detection

task will be conducted. Tests will be conducted in the soundfield with the better ear plugged for soft (35 dB) and average (50 dB) speech inputs at speech front, noise front (0°/0° azimuth)

- Aim 3b

Pediatric bilateral conductive hearing loss patients who are between the ages of 2 and 17 years of age and are currently managed by the UMEI with a bone conduction device attached to a softband will be enrolled for study. Subjects will be given the ADHEAR bone conduction system on trial for 4 weeks ± 7 days. Subjects will be evaluated over 3-4 experimental visits.

- VISIT 1: Assessment of subject's bone conduction device on softband and initiation of ADHEAR trial
  - Prior to dispensing of the experimental system, function of the subject's current bone conduction device will be verified.
  - Subjective measures will be administered to determine benefit and satisfaction with the subject's own device on the softband.
  - Subjects will undergo behavioral measures of benefit with own bone conduction device on a softband. It is anticipated that the majority of bilateral conductive hearing loss subjects will be unilaterally fitted. Subjects will be tested in their everyday listening condition
  - Subjects will be provided ADHEAR bone conduction hearing system unilaterally
  - In those who are bilaterally fit with a bone conduction device, testing will be conducted unilaterally. To maintain the child's everyday listening condition, participants will be fit with 2 ADHEARs (i.e. bilateral). T
- VISIT 2 (2 weeks ± 90 days):
  - Subjective measures will be administered to determine benefit and satisfaction with the ADHEAR bone conduction hearing system
  - Subjects will undergo behavioral measures of benefit with ADHEAR bone conduction hearing system unilaterally
  - Subjects will be provided ADHEAR bone conduction hearing system bilaterally
  - In those who are bilaterally fit at time of enrollment, testing will be conducted bilaterally with the ADHEARs, and trial will discontinue.
- VISIT 3 (4 weeks ± 90 days):
  - Subjective measures will be administered to determine benefit and satisfaction with the ADHEAR bone conduction hearing system
  - Subjects will undergo behavioral measures of benefit with ADHEAR bone conduction hearing system bilaterally
  - Time and subject permitting subjects will be tested in bilateral softband condition, otherwise this will be completed in an additional visit (4)

Objective and behavioral outcome measures bilateral conductive hearing loss subjects:

- Data logging of device use (parent and subject report)
- Soundfield aided narrowband signal thresholds bilaterally aided
- Soundfield aided Ling thresholds using the DSLio - Ling 6(HL) test (v2.0) which provides calibrated, pre-recorded Ling 6 sounds (m, u, a, i, sh, s) for use in measuring unaided or aided thresholds.
- Soundfield aided speech reception thresholds
- Word recognition ability using the Auditec Inc PBK-50 words under bilaterally aided conditions. Tests will be conducted in the soundfield with the better earplugged for

soft (35 dB) and average (50 dB) speech inputs at speech front, noise front (0°/0° azimuth)

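### The ±90-day tolerance is longer than the 2-, 3- and 4-week intervals it qualifies, so those windows set no minimum ADHEAR wear, and Aim 3b gives two inconsistent timings

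*Combined protocol and SAP*

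**What the plan says.** Study Design states a trial period or visit time for each aim. Aims 1&2 give the Adhear for 2 weeks, Aim 3 Phase 1 runs for 3 weeks, and in Aim 3a "Subjects will be given the ADHEAR bone conduction system on trial for 2 weeks". All three carry ±90 days. Aim 3 Phase 2 has no duration of its own.

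In Aim 3b the opening statement is tighter: "Subjects will be given the ADHEAR bone conduction system on trial for 4 weeks ± 7 days". The visit list that follows returns to the wide tolerance, with "VISIT 2 (2 weeks ± 90 days" and then "VISIT 3 (4 weeks ± 90 days".

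For most Aim 3b children, who are expected to be unilaterally fitted, the second ADHEAR arrives at Visit 2 ("Subjects will be provided ADHEAR bone conduction hearing system bilaterally") and is tested at Visit 3 ("Subjects will undergo behavioral measures of benefit with ADHEAR bone conduction hearing system bilaterally"). Children already bilaterally fitted receive two ADHEARs at Visit 1, are tested bilaterally at Visit 2, and stop there.

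Data Management summarises the questionnaires by visit and tests change from baseline for numeric measures. Hours of use are collected, but no section sets a minimum number of days or hours of ADHEAR wear. The six-month experience rule in the eligibility criteria concerns the adults' existing implants.

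**The concern.** A visit window should keep the exposure behind a labelled result close to its label. Here the early side does nothing, and the late side extends beyond three months. A test or questionnaire reported as 2, 3 or 4 weeks could therefore follow very short wear or very long wear, and the plan does not say that results will be shown against actual wear.

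This matters most in Aim 3a and in the Visit 1 versus ADHEAR contrasts of Aim 3b. There the child's own device is always tested first, the ADHEAR later, and the gap is loosely controlled in children as young as 2. Study Populations sets minimum group sizes of only 15 unilateral and 10 bilateral children, so a few off-schedule visits could affect a group summary.

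In Aim 3b the two timing statements also disagree. A Visit 3 on day 60 is in window by the visit list and past the end of the trial by the opening statement, although the device under test at that visit is the one on trial.

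**Working it through.** Take day 0 as dispensing, with lower limit = nominal − tolerance and upper limit = nominal + tolerance. All inputs are from Study Design.

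| Interval | Where | Lower limit | Upper limit | Tolerance ÷ interval |
|---|---|---|---|---|
| 14 ± 90 days | Aims 1&2, Aim 3a, Aim 3b Visit 2 | 14 − 90 = −76 | 14 + 90 = 104 | 6.4 |
| 21 ± 90 days | Aim 3 Phase 1 | 21 − 90 = −69 | 21 + 90 = 111 | 4.3 |
| 28 ± 90 days | Aim 3b Visit 3 | 28 − 90 = −62 | 28 + 90 = 118 | 3.2 |
| 28 ± 7 days | Aim 3b, whole trial | 28 − 7 = 21 | 28 + 7 = 35 | 0.25 |

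The negative limits cannot occur in practice; they show only that the early side of the window does not bind. The last row is the one interval with a positive minimum.

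**Aim 3b, one statement against the other.** Visit 3 on days 36 to 118 is allowed by the visit list but lies beyond day 35, by up to 118 − 35 = 83 days. Visit 2 alone may fall up to 104 − 35 = 69 days beyond it.

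**Bilateral wear before the Visit 3 test**, for children who receive the second ADHEAR at Visit 2 (Visit 3 day − Visit 2 day, assuming visits at least 1 day apart):
- Nominal: 28 − 14 = 14 days.
- Both statements met (Visit 3 on days 21 to 35): minimum 1, maximum 35 − 1 = 34 days.
- Visit list alone: minimum 1, maximum 118 − 1 = 117 days.

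These are the extremes that the wording permits, not a forecast of what the clinic will do.

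**Children bilaterally fitted at enrolment.** Their trial ends at Visit 2, nominally day 14, which is 21 − 14 = 7 days short of the minimum in the 4-week statement. The Visit 3 figures above do not apply to them.

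**Longest gap from own-device test to ADHEAR test:** 104 days in Aim 3a and at Aim 3b Visit 2; 118 days at Aim 3b Visit 3.

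**The case against.** The strongest reply is that this is untidy wording with little consequence. Much of it stands.

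- **The two Aim 3b statements can both be followed.** A reader might infer that they are irreconcilable. They are not: Visit 3 on days 21 to 35 satisfies both, and total ADHEAR wear then has a 21-day floor. What remains is that the statements disagree and that no minimum separates the bilateral fitting from the bilateral test.
- **Some wear is implied.** A reader might infer that testing on the day of dispensing is planned. The text points the other way, with separate visits ("Subjects will be evaluated over 2 experimental visits" in Aim 3a, "Subjects will be evaluated over 3-4 experimental visits" in Aim 3b). The gap is that no minimum is written.
- **Many contrasts hardly depend on the window.** A reader might infer that the device comparisons are biased throughout. In Aims 1&2 the Adhear is tested beside the implant at the first session and beside the subject's own processor on a soft headband at follow-up. In Aim 3 device order is randomised, so unequal wear mainly adds variability. In Aim 3b a bilateral softband test may take place at Visit 3 beside the bilateral ADHEAR.
- **No effect of wear time is documented.** Many outcomes are aided thresholds, and nothing in the protocol says that they change with wear.
- **Spread in use would be visible.** Hours of use are collected and quantitative data are shown as mean, SD and range, though not tied to each contrast.

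The mention of COVID-19 does not answer the point. Subjective outcome measures invokes it for telephone questionnaires and does not link it to the ±90 days. Scheduling difficulty would justify late visits, not a 90-day early allowance.

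**Conclusion.** The point holds in a limited form and should be corrected. As written, the ±90-day windows impose no minimum wear and permit tests up to days 104, 111 and 118. The two Aim 3b timings are inconsistent, and the 4-week length does not fit children whose trial ends at Visit 2.

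The arithmetic is certain, given day 0 at dispensing; the bilateral-wear ranges also assume visits on separate days. Counting Visit 3 from Visit 2 instead of Visit 1 would not remove the inconsistency.

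The impact is narrow: Aim 3a, the own-device versus ADHEAR contrasts of Aim 3b that start from Visit 1, and questionnaire results labelled by visit. The documents support no estimate of the size or direction of any distortion. Nor should the fixed test order in Aims 3a and 3b be attributed to the windows: tightening them would make the gap more uniform but leave the order as it is.

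**What to change.** 1. Replace ±90 days with asymmetric windows that have a positive minimum after dispensing. As an example, the lower tolerance in the Aim 3b opening statement is 7 ÷ 28 = 25%. Applied throughout, it gives 0.75 × 14 = 10.5, rounded up to day 11; 0.75 × 21 = 15.75, rounded up to day 16; and 0.75 × 28 = day 21. Late tolerance may stay wider if clinic scheduling needs it.
2. For Aim 3b children who continue to Visit 3, state the same window in the opening paragraph and the visit list, and hold Visit 3 at least 11 days after the bilateral fitting. The earliest case works: Visit 2 on day 11 puts Visit 3 at day 22 or later, past the day-21 minimum. If day 35 stays as the upper limit, Visit 2 must be by 35 − 11 = day 24; otherwise raise the upper limit in the opening paragraph.
3. For children bilaterally fitted at enrolment, state a 2-week trial ending at Visit 2, with the same 2-week minimum.
4. Report actual days and hours of wear, by device, beside each contrast.

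The cost is a short wording amendment and one descriptive table. Hours of use are already collected; visit dates are not among the items listed in Data Management, so a date field per visit may be needed. The downside is that some early visits become out of window.
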